### **7.2. Duration of Exposure to Study Drug**

Duration of exposure to study drug (days) for individual patients is the number of days patient received drug (last day of study drug – first day of study drug + 1). Duration of treatment (days) will be summarized using descriptive statistics. Years on treatment using the categories  $\leq 1$  year,  $>1$  to  $\leq 2$  years,  $>2$  to  $\leq 3$  years,  $>3$  to  $\leq 4$  years,  $>4$  to  $\leq 5$  years,  $>5$  to  $\leq 6$  years, and  $>6$  years will also be summarized using descriptive statistics.

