#### **5.3.1 Dose Frequency Reduction**

In the event of tolerability problems, patients will be instructed to immediately contact their investigator (or qualified designee) to discuss their AEs. The investigator (or qualified designee) will assess whether or not the AEs could be related to IMP and severe enough to warrant a dose frequency reduction. The patients will be instructed to stop taking 1 of the 2 capsules of their daily dose. Arrangements for an USV at the earliest opportunity will be made (see Section 4.6.5). At this visit patients will be provided with instructions regarding the de-escalated dose frequency. Alternatively, patients may be temporarily off drug up to 60 days per year in the event of tolerability problems, as judged by the investigator (or qualified designee).

---

IMP re-introduction or dose frequency increase back to the previous dose frequency may be considered if the clinical monitor, investigator (or qualified designee), and the patient agree that this should be attempted. Alternatively, qd dosing may be maintained.

Patients should be advised that if tolerability problems continue then they should contact their investigator (or qualified designee) who may then withdraw them from IMP (see Section 7.7.2 for withdrawal procedures).

IMP must be reduced to 45 mg qd for the following events:

- Any QTcF increase >60 ms from the first remote visit
- QTcF  $\geq$ 480 ms and  $\leq$ 500 ms
- Creatinine clearance <60 mL/min and >40 mL/min

If an IMP must be reduced to 45 mg qd and the patient is not currently at a study visit arrangements for an USV at the earliest opportunity will be made (see Section 4.6.5). At this visit, patients will be provided with instructions regarding the de-escalated dose frequency.

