## **8.9 Assessments and Analysis of Safety and Tolerability**

### **8.9.1 Exposure**

The overall exposure in terms of patient-years will be presented by treatment. The number of patients who had a dosage reduction and who had a suspension of IMP will be presented.

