At **Visit 1 (1 Month)** the following will be documented: an evaluation for research study consent, review of concomitant medications (including inquiry about changes in use of benzodiazepines and antidepressants); inquiry about changes in use of alcohol and illicit drugs, AEs, C-SSRS, PBA-s, vital signs and drug compliance. Evaluation for Research Study Consent, ECG and blood draw (calcium, magnesium, potassium, and creatinine for creatinine clearance calculation) will be performed for patients from the PRIDE-HD study.

Subsequently, the patient will be contacted every 3 months as per below:

At **Telephone or in-person Visits [Safety Visit (SV)] (eg after 3, 9, 15 months etc.)** the following will be documented: an evaluation for research study consent, review of concomitant medication (including inquiry about changes in use of benzodiazepines and antidepressants); inquiry about changes in use of alcohol and illicit drugs, C-SSRS and PBA-s assessment, review of AEs, and assessment of compliance with trial medication. A 12-lead ECG will be obtained, vital signs will be assessed and calcium, magnesium and potassium level and creatinine for

creatinine clearance calculation will be drawn [hypokalemia is defined as a potassium level less than 3.5 mEq/L]. If less than 3.5 mEq/L, patient's study drug will be suspended until normal (greater than or equal to 3.5mEq/L). Participants can choose to have the assessments of vital signs, ECG and blood draw for calcium, magnesium, potassium, and creatinine for creatinine clearance calculation performed by their GP and/or local cardiologist or schedule a visit with site but the site must have a telephone contact with the participant to review concomitant medication, AEs and assess compliance with trial medication.

At **Telephone contacts [C] (eg once a month between on-site visits)** the following will be documented: an evaluation for research study consent, review of concomitant medication (including inquiry about changes in use of benzodiazepines and antidepressants); inquiry about changes in use of alcohol and illicit drugs, review of adverse events, C-SSRS and an abbreviated PBA-s assessment.

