### **7.3. Adverse Events**

All AEs will be coded using the MedDRA. AEs occurring on or after the first day of study drug administration will be included in the summaries. Summaries will be presented for all AEs (overall and by severity), AEs determined by the investigator to be related to study drug (overall and by severity), serious AEs, AEs leading to withdrawal from the study, and non-serious AEs.

The incidence and total number of AEs will be summarized using descriptive statistics by SOC and PT (all AEs overall will also be presented by just PT category). For the incidence of AEs, patients are counted only once in each SOC category, and only once in each PT category. The exposure adjusted incidence rate will also be presented and is defined as the number of patients with an AE divided by patient-years of treatment. For calculating patient-years, patients with an AE contribute with treatment exposure up to the day of their first AE, and patients without an AE contribute with the entire treatment exposure. For the summary by severity, patients are counted at the greatest severity. AEs missing relationship to study drug will be included in the study drug related summary.

In addition, a summary of AEs by time period of treatment will be presented.

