## **8. STATISTICAL SOFTWARE**

All data listings, summaries, and statistical analyses will be generated using SAS® version 9.4 or later.

**9. CHANGES TO ANALYSES SPECIFIED IN THE STUDY  
PROTOCOL**

There are no changes to analyses specified in the study protocol.

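### SAP 7.2 labels the first-to-last-dose calendar span as days on drug, so planned interruptions count as exposure, and it drops the suspension and dose-reduction counts found in Protocol 8.9.1

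*SAP*

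**What the plan says.** SAP Section 7.2 describes a patient's duration of exposure as the "number of days patient received drug (last day of study drug", with the first day subtracted and 1 added. The result is summarised in days and in yearly categories running from one year or less to more than six years.

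The same SAP plans for time off drug. Under Section 2.1, if potassium is below 3.5 mEq/L, the "patient's study drug will be suspended until normal". The section on unscheduled visits also foresees de-escalation. In the supplied protocol, Section 5.3.1 adds that "patients may be temporarily off drug up to 60 days per year in the event of tolerability problems" and allows once-daily dosing to continue.

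Protocol Section 8.9.1 states: "The number of patients who had a dosage reduction and who had a suspension of IMP will be presented". SAP 7.2 has no such display, and no other SAP section supplies one. SAP Section 9 says: "There are no changes to analyses specified in the study protocol".

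SAP Section 7.3 uses exposure again in the adverse event (AE) rate, "defined as the number of patients with an AE divided by patient-years of treatment". For the denominator, "patients with an AE contribute with treatment exposure up to the day of their first AE", while "patients without an AE contribute with the entire treatment exposure". No rule is given for gaps in dosing.

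**The concern.** The label and the formula in SAP 7.2 describe different quantities. Last day minus first day plus 1 counts every calendar day between the two doses, including days on which the plan itself requires or permits no drug. Long-term safety is part of the primary objective, and the years-on-treatment table is where a reader will look to see how long patients took pridopidine.

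A calendar span is a common and usable measure if it is named as such and shown with interruption data. Here it is named as days on drug and the interruption data are absent. The reader can neither correct for the gaps nor see how many patients were suspended or reduced to once-daily dosing.

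**Working it through.** The documents state no exposure total or rate, so there is no planned figure to reproduce. The check is how far the formula can depart from its label.

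**Inputs**
- Formula: last day − first day + 1 (SAP 7.2).
- Low-potassium suspension: SAP 2.1 gives no length. Protocol 6.3.2 requires normal values held for 7 days before restart, and withdrawal from drug if stability takes more than 14 days.
- Tolerability allowance: up to 60 days per year (Protocol 5.3.1, Amendment 05 text).
- Frequency and length of actual interruptions: not given, so varied below as assumptions.

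**One patient, d days off per 365.25-day year.** Overstatement = 365.25 / (365.25 − d) − 1.

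| Days off per year | Days on drug | Overstatement |
|---|---|---|
| 7 | 358.25 | 2.0% |
| 14 | 351.25 | 4.0% |
| 30 | 335.25 | 8.9% |
| 60 (ceiling) | 305.25 | 19.7% |

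**Year categories at the ceiling.** A 6-year span is 6 × 305.25/365.25 = 5.01 years on drug. A 6.5-year span is 5.43 years, so that patient is shown as more than 6 years when time on drug falls in the 5-to-6-year category.

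**Pooled patient-years.** If a share p of patients, with equal spans, each has d days off per year, the overstatement is 1 / (1 − p × d/365.25) − 1. For d = 60: p = 10% gives 1.7%, 25% gives 4.3%, 50% gives 8.9%. For d = 14 and p = 25%, it is 1.0%.

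**Once-daily periods.** A year of once-daily dosing is still 365 days on drug, so duration does not change. Cumulative dose does: 45 × 365 = 16,425 mg against 90 × 365 = 32,850 mg.

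**Effect on the AE rate** (illustration with assumed figures). Take 20 patients with a first AE at 1 year and 27 without an AE over 4 years. Patient-years = 20 × 1 + 27 × 4 = 128; rate = 20/128 = 0.156.
- Gaps only after the first AE: denominator unchanged, rate 0.156.
- 60 days per year off in all patients without an AE: 20 / (20 + 108 × 305.25/365.25) = 0.181.
- 60 days per year off in everyone: 20 / (128 × 305.25/365.25) = 0.187.
- As the previous line, but AEs starting off drug also removed from the numerator, patient-years otherwise held: 17/106.97 = 0.159 with 3 removed, 16/106.97 = 0.150 with 4 removed.

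The corrected rate can therefore lie above or below the SAP's 0.156, depending on how AEs that start in gaps are treated.

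**The case against.** **The rate.** A reader might infer that AE rates are understated by up to 16.4% (1 − 305.25/365.25), and most so in the patients who have events. The documents do not support this. SAP 7.3 stops a patient's exposure at the first AE, so a gap prompted by that AE adds nothing to its denominator; it matters only for other preferred terms. The numerator takes every AE from first dose on, with no end date and no exclusion of gaps. Within the treatment span, calendar time matches that numerator, and subtracting gap days from the denominator alone would create a mismatch. AEs after the last dose enter with no matching exposure, which pushes the rate up. Protocol 7.1.3 also counts events within the time of residual drug effect as treatment-emergent, so short gaps are not free of risk. This objection stands in full.

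**Once-daily dosing.** A reader might also count once-daily days as inflated exposure. They are days on which drug was received. What is missing is reporting of dose intensity.

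**Protocol version.** The 60-day allowance and Section 8.9.1 are in Amendment 05 text. SAP 2.1 says the SAP follows Amendment 04 and that Amendment 05 was not implemented. This limits the 19.7% figure and the comparison with 8.9.1. It does not touch the core point, because the potassium suspension and the de-escalation are in the SAP's own design section.

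**Size.** The ceiling needs a patient to use the whole allowance, and continuing tolerability problems may lead to withdrawal from drug instead. The study is descriptive, with no threshold to cross. Both are fair, and they make the point modest, but they do not make the label correct.

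**Conclusion.** The plan is wrong as written on a narrow point. SAP 7.2 does not calculate what it says it calculates, and the error in duration and in the year categories runs one way only, upward. For an affected patient it is about 4% with 14 days off per year and at most 19.7% at the 60-day ceiling, if that allowance was in force. The pooled effect is probably a few percent; this rests on an assumed share of patients interrupting, for which the documents give no figure.

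Dose intensity goes unreported because the suspension and dose-reduction counts in Protocol 8.9.1 are absent from the SAP. It would be tempting to conclude that the statement in SAP Section 9 is false. That cannot be confirmed, because the current text does not show whether Amendment 04 worded 8.9.1 the same way.

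No direction of bias in the exposure-adjusted AE rates is established.

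**What to change.** - **SAP 7.2:** rename the existing formula *time from first to last dose*. Add *days on drug*, net of recorded interruptions, and use it for the years-on-treatment table.
- **SAP 7.2:** add the numbers of patients with a dosage reduction and with a suspension, and patient-years by dose frequency where recorded.
- **SAP 7.3:** use the same time window for the AE numerator and the patient-year denominator, and say how AEs starting in gaps or after the last dose are handled. Show any rate based on net exposure as a sensitivity analysis.
- **SAP 9:** check against the protocol version in force and correct if needed.

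The cost is SAP wording and programming, and reported time on drug becomes slightly shorter. The net figure depends on interruption dates having been captured. The AE log has an action-taken category (Protocol 7.2.2.4) but lists no interruption start and stop dates, compliance is by inquiry and capsule count (Protocol 5.6), and the drug diary mentioned in SAP 4.5 is not described. If dates prove incomplete, the renaming and the two counts are still worth making.

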### **7.3. Adverse Events**

All AEs will be coded using the MedDRA. AEs occurring on or after the first day of study drug administration will be included in the summaries. Summaries will be presented for all AEs (overall and by severity), AEs determined by the investigator to be related to study drug (overall and by severity), serious AEs, AEs leading to withdrawal from the study, and non-serious AEs.

The incidence and total number of AEs will be summarized using descriptive statistics by SOC and PT (all AEs overall will also be presented by just PT category). For the incidence of AEs, patients are counted only once in each SOC category, and only once in each PT category. The exposure adjusted incidence rate will also be presented and is defined as the number of patients with an AE divided by patient-years of treatment. For calculating patient-years, patients with an AE contribute with treatment exposure up to the day of their first AE, and patients without an AE contribute with the entire treatment exposure. For the summary by severity, patients are counted at the greatest severity. AEs missing relationship to study drug will be included in the study drug related summary.

In addition, a summary of AEs by time period of treatment will be presented.

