#### **Withdrawal from treatment**

If the patient wishes to stop the drug, or is judged by the investigator to not be suitable for continued therapy, or the study is discontinued, a clinic visit ("withdrawal visit", end of study drug visit) should be performed and the patient withdrawn from the study. A (telephone) follow-up visit (30 d TC F/U) to collect and report AEs (as well as inquiry about changes in use of benzodiazepines and antidepressants, and inquiry about changes in use of alcohol and illicit drugs), C-SSRS and an abbreviated PBA-s assessment should take place one month after the actual discontinuation of study drug took place.

Patients who discontinue study medication due to safety or tolerability reasons may continue in the study off drug and perform the scheduled visits and assessments.

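### The exposure-adjusted AE rate in SAP 7.3 counts events that start after the last dose but leaves out the off-drug time at risk

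*SAP*

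**What the plan says.** **Events counted.** SAP 7.3: "AEs occurring on or after the first day of study drug administration will be included in the summaries". No upper limit after the last dose is given.

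**Person-time.** SAP 7.3 describes the rate as "defined as the number of patients with an AE divided by patient-years of treatment". It adds: "For calculating patient-years, patients with an AE contribute with treatment exposure up to the day of their first AE"; patients without an AE contribute all of their treatment exposure. SAP 7.2 calculates a patient's exposure as "last day of study drug – first day of study drug + 1", so it stops at the last dose.

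**AE collection off drug.** SAP 2.1, under Withdrawal from treatment, plans "A (telephone) follow-up visit (30 d TC F/U) to collect and report AEs", which "should take place one month after the actual discontinuation of study drug took place". Patients who come off drug on safety or tolerability grounds "may continue in the study off drug and perform the scheduled visits and assessments". AE review is part of those visits.

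**Stopping tables.** The only AE table in SAP 7.3 tied to stopping is for "AEs leading to withdrawal from the study". SAP 5.2 counts withdrawals from treatment and from study, with reasons, but not by SOC and PT.

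**The concern.** Events and time at risk have to cover the same period for the ratio to be a rate. Here the event window is open-ended and the person-time window closes at the last dose. A patient whose first event in an SOC or PT begins off drug adds one to the numerator and no off-drug time to the denominator.

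Long-term safety is a primary objective and there is one arm. Each SOC/PT rate is therefore read as an absolute figure, with no control arm in which the same distortion would be visible. The any-AE rate should be affected less, because most patients who stop for safety already have a counted event. The summary by time period of treatment defines no off-drug period, so it does not clearly separate these events.

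A secondary gap concerns patients who stop drug for an AE and remain on study. Their events appear in the all-AE tables, but no SOC/PT table marks them as the reason for stopping drug.

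**Working it through.** The SAP states no rate, so there is no figure to reproduce. The check has two steps: a count that shows the mechanism, and a model that shows its size.

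**Step 1: mechanism.** Ten patients are each treated for 2 years. Two have a first event on drug at year 1. Two others have a first event 0.5 year after the last dose.

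- Person-time under SAP 7.3: 2×1 + 8×2 = 18 years.
- SAP rate: 4/18 = 0.222 per patient-year.
- On-treatment events over on-treatment time: 2/18 = 0.111.
- All events over all time to first event, adding only the off-drug time of the two late cases: 4/(18 + 2×0.5) = 4/19 = 0.211.

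The last two are each internally consistent. The SAP rate is not.

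**Step 2: size.** All inputs are assumptions; the documents give none of them.

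- On-drug hazard h = 0.10 per year, constant, and stopping unrelated to the event.
- 20% of patients stop at year 1; the rest are treated to year 4.
- A share q of stoppers stays on study off drug to year 4. The others have only the call at f = 30/365 year.
- Off-drug hazard = r × h.

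On-drug event probability by t is F(t) = 1 − e^(−0.1t), so F(1) = 0.09516 and F(4) = 0.32968.

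Person-years per patient under the SAP = [0.8×0.32968 + 0.2×0.09516]/0.10 = 2.8278.

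Numerator per patient = 0.8×0.32968 + 0.2×[q×(1 − e^(−0.1−0.3r)) + (1−q)×(1 − e^(−0.1−0.1rf))].

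For q = 0.25 and r = 1: 0.26374 + 0.2×[0.25×0.32968 + 0.75×0.10257] = 0.29561. The rate is 0.29561/2.8278 = 0.1045 against a true 0.1000, or +4.5%.

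Effect of the off/on hazard ratio, q = 0.25:

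| r | Numerator | Rate | Excess |
|---|---|---|---|
| 0 | 0.28278 | 0.1000 | 0% |
| 0.25 | 0.28632 | 0.1013 | +1.3% |
| 0.5 | 0.28963 | 0.1024 | +2.4% |
| 1 | 0.29561 | 0.1045 | +4.5% |
| 1.5 | 0.30083 | 0.1064 | +6.4% |

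Effect of the share who stay, r = 1:

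| q | Excess | Excess if the call is also counted for those treated to year 4 |
|---|---|---|
| 0 | +0.5% | +2.1% |
| 0.25 | +4.5% | +6.1% |
| 0.5 | +8.6% | +10.1% |
| 1 | +16.6% | +18.1% |

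Other settings, r = 1:

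- 10% stop at year 2: +1.3% if a quarter stay, +4.7% if all stay.
- First scenario with q = 0.25: +4.7% at h = 0.05 and +4.0% at h = 0.30, so the hazard level matters little.
- 30-day call only, all treated equally long, h = 0.10: F(4+f)/F(4) − 1 = +1.7%; F(6+f)/F(6) − 1 = +1.0%. With 1 year of treatment the same calculation gives +7% to +8% for hazards of 0.02 to 0.2.
- All treated 2 years, 20% then staying 2 years off drug, h = 0.05: [0.8×0.09887 + 0.2×0.18127]/[0.09516/0.05] = 0.0606, or +21%.

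**Sampling error for scale.** With 47 patients (the Amendment 05 synopsis; the SAP gives no number treated), 47×0.29561 = 13.9 have the event and the relative standard error is about 1/√13.9 = 27%. With 200 patients it would be 1/√59.1 = 13%.

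**Check of the fix.** A 14-day residual period serves here only as a placeholder. Applied to both events and person-time, it returns 0.1000. Applied to events only, the numerator is 0.8×0.33225 + 0.2×0.09863 = 0.28553 and the excess is still 0.28553/0.28278 − 1 = +1.0%. Both sides have to change.

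**The case against.** The strongest reply is that little turns on this. The analysis is descriptive, crude incidence stands beside the rate, and any distortion overstates harm, which is the cautious direction. An upward bias also requires that events occur off drug: with none, it is zero. The largest illustrated figures need every stopper to stay off drug for three years, which nothing in the documents supports. Counting interruptions as exposure, as the SAP 7.2 formula does, pulls the rate down. All of this stands and limits the size. It does not make the definition coherent, and a downward imprecision of unknown size does not correct an upward one.

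A reader might infer that the SAP dropped a two-week limit set by the protocol. The documents do not support that. In Protocol 8.9.2 the two weeks apply to AEs that began earlier, in Open-HART or Open-PRIDE-HD, and are still continuing. For events starting in the virtualized period that section sets no end date either. Protocol 7.1.3 uses residual drug effect instead. Protocol 8.9.2 also plans rates per exposure, so dividing by exposure is not itself a departure. In any case this protocol text is Amendment 05, which SAP 2.1 says was not implemented. The SAP follows Amendment 04, which is not among the documents, so whether it departs from its own protocol cannot be settled.

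On the stopping table, a reader might infer that AEs which end treatment go unreported. That is too strong. Under SAP 2.1 the default on stopping drug is withdrawal from the study, which the planned table covers, and SAP 5.2 reports the reasons for stopping treatment. Only patients who stop drug for an AE and stay on study are missed, and their number is unknown.

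**Conclusion.** The mismatch stands on the SAP alone (2.1, 7.2 and 7.3): the rate is wrong as defined and is overstated to the extent that first events occur off drug. With a quarter of stoppers staying on study, the first scenario gives 0% to about +6% for off/on hazard ratios of 0 to 1.5. More patients staying, shorter treatment, or counting the call for those treated to year 4 raises it. These are illustrations under a constant hazard and stopping unrelated to the event, not estimates for this trial.

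It would be tempting to call this a material distortion of the safety results, or to dismiss it as always below sampling error. Neither is supported, since the number treated, the share off drug and the off-drug event rate are not given. It is a modest reporting bias and threatens no test. The missing SOC/PT table is a narrower, secondary gap.

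**What to change.** In SAP 7.3, before database lock:

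1. Define one on-treatment window, from first dose to last dose plus a residual period that the sponsor states and justifies. Check it against Amendment 04. Do not present 14 days as the protocol's rule.
2. Apply that window to both the events and the person-time of the exposure-adjusted rate.
3. Show AEs with later onset in a separate display.
4. Optional: add an SOC/PT table of AEs leading to discontinuation of study drug, whether or not the patient stayed on study.

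The cost is one or two sentences, one display of late-onset AEs and, if adopted, one table. No new data are needed for that table if the action taken with study drug was recorded for each AE. The downside is that late-onset AEs leave the main rate table and have to be read from the separate display.

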### **5.2. Patient Disposition**

Patient screened, patients screened but not in the ITT analysis set (and reason not in the ITT analysis set) will be summarized using patient counts. Patients in the ITT analysis set, patients in the ITT analysis set but not treated, patients in the safety and full analysis sets, patients who completed treatment and completed study, and patients who withdraw from the treatment and study (and reasons for withdrawing) will be summarized using descriptive statistics.

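### SAP 7.3 tabulates adverse events that led to leaving the study, but not those that led to stopping study drug

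*SAP*

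**What the plan says.** SAP 7.3 lists AE summaries for all AEs, for AEs the investigator judged related to study drug, for serious AEs, and for "AEs leading to withdrawal from the study, and non-serious AEs". It adds a summary by time period on treatment. On format it says: "The incidence and total number of AEs will be summarized using descriptive statistics by SOC and PT". An exposure-adjusted incidence rate is also planned, "defined as the number of patients with an AE divided by patient-years of treatment". Patients with an event contribute exposure up to their first event.

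SAP 2.1, under the heading on withdrawal from treatment, says: "Patients who discontinue study medication due to safety or tolerability reasons may continue in the study off drug". The paragraph before it says that a patient who wishes to stop, or is judged unsuitable for further therapy, has a withdrawal visit and is withdrawn from the study.

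SAP 5.2 covers "patients who completed treatment and completed study", and also "patients who withdraw from the treatment and study (and reasons for withdrawing"). SAP 7.2 derives exposure as "the number of days patient received drug". SAP 8 says only that "All data listings, summaries, and statistical analyses will be generated" with the named software; no individual listing is specified.

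**The concern.** Stopping drug and leaving the study are separate outcomes in this design, and AEs are tabulated against only the second. The patients allowed to stay without drug are those who stopped for safety or tolerability reasons, which is where treatment-ending AEs are to be expected.

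Long-term safety is part of the primary objective (SAP 1), and with one arm and no inferential analysis the safety tables are the main product of the study. A reader who asks which events ended long-term treatment, and at what rate, may get an incomplete answer from a table that looks as though it answers the question.

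**Working it through.** The plan gives no figure on this point, and none can be derived. The check sets the sections of the SAP side by side.

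**1. Planned AE selections (SAP 7.3).**

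| AE summary | Selects on stopping study drug? |
|---|---|
| All AEs | No |
| Drug-related AEs | No |
| Serious AEs | No |
| AEs leading to withdrawal from the study | No; selects on leaving the study |
| Non-serious AEs | No |

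That is 0 of 5. The additional summary by time period does not select on stopping drug either, and SAP 7.4 to 7.8 add no such summary.

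**2. Whether leaving the study can stand for stopping drug.** Let D be the patients who stop drug because of an AE, and W those who leave the study because of an AE. The table planned in 7.3 describes W. It would cover D only if every patient in D were also in W. The permission in SAP 2.1 to remain enrolled without drug means this need not hold. SAP 5.2 names both treatment and study for completion and for withdrawal, so the SAP itself keeps the two apart.

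**3. Size of the gap.** Gap = number of patients in D but not in W, that is, those who stop drug for an AE and remain. The minimum is 0. The documents give neither D nor the overlap.

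**4. Whether other outputs fill the gap.**
- The general AE tables contain the event, by SOC and PT and with a rate, but do not mark it as having ended treatment.
- Disposition gives the number withdrawing from treatment with reasons, but no SOC or PT terms and no rate.
- Listings are mentioned in SAP 8 but not specified. If the AE listing shows action taken on study drug, cases can be found one by one. What is lost is then the tabulation and the rate, not the data.

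**5. A possible misattribution.** SAP 7.3 includes AEs from the first day of drug onward and states no end to the window. A patient could stop drug for one event, stay, and later leave the study for another. The planned table would show the second event and omit the first. The rules permit this; nothing in the documents shows that it occurred.

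**6. Protocol version.** SAP 2.1 says that the SAP follows Amendment 04 and that Amendment 05 was not implemented. The supplied protocol is Amendment 05. Steps 1 to 5 therefore use the SAP alone. Protocol 8.9.2 plans displays of AEs leading to discontinuation without saying of what, so it cannot settle the matter and is not relied on.

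**The case against.** The best counter-argument is that the SAP may be using its terms loosely. The withdrawal paragraph in SAP 2.1 uses one visit for both the end of study drug and withdrawal, and its first rule takes patients who stop drug out of the study. Remaining enrolled is an option stated afterwards. On that reading the 7.3 table may have been meant to cover stopping drug.

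The supplied protocol gives this some support. Among the AE log items in protocol 7.2.1, the one tied to stopping is action taken on study drug. No item is dedicated to an AE having led to study withdrawal. A table built from that log alone would in practice select on drug discontinuation.

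Two further points are fair. A treatment-ending AE still enters the all-AE tables, and the related or serious tables where it qualifies. And a rate by SOC and PT over very few patients adds little to a count.

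What stands is that the first rule in SAP 2.1 makes the gap smaller, that the CRF in use cannot be seen, and that the number affected may be nil. None of this removes the gap. The SAP permits patients to stay without drug, and a programmer following 7.3 as written would select on study withdrawal. If the intended table is the other one, the text still needs correcting. The rate is the one 7.3 already applies, so including it keeps the new table consistent with the others.

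**Conclusion.** The concern holds on the SAP text alone. No AE summary in 7.3 selects on discontinuation of study drug, the one stopping-related table is defined by leaving the study, and the SAP allows patients to do the first without the second.

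The size is unknown and may be zero. No comparison or inference is affected; what is incomplete is the description of which AEs ended treatment. The change should be made because it bears on the primary safety objective and costs little. The conclusion takes study withdrawal in 7.3 at its plain meaning. The proposed selection further assumes that the CRF in use records action taken on study drug, as the supplied protocol does in 7.2.2.4.

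**What to change.** In SAP 7.3:

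- Add a summary by SOC and PT of AEs whose action taken on study drug is recorded as discontinued, whether or not the patient remains in the study. Give incidence, number of events and the exposure-adjusted rate as 7.3 already defines it.
- Keep the table of AEs leading to study withdrawal as a separate output, and name the data item that selects each table.
- If the Amendment 04 protocol also refers to AEs leading to discontinuation without saying of what, state how the two tables relate to that term.

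The two statements in SAP 2.1 on what happens to a patient who stops drug should also be reconciled, so that it is clear which patients belong in which table.

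The cost is one line of text and one extra table. Exposure is already derived under 7.2 and the patient-years rule is already in 7.3. No new data are needed if the CRF carries the action-taken item. SAP 2.6.2 provides for amendments approved before database lock.
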